7.3 Tumor Tissue Biopsies

Fresh and archival tumor tissue will be submitted for laboratory analysis to understand the basis for response or resistance to treatment. Fresh and archival tumor (if available) samples are a requirement for participation in the study. However, patients who do not have easily accessible tumor for biopsy should not be put at undue risk for sample collection and these patients remain eligible for the study. Biopsied lesions must not be designated as target lesions for the purposes of RECIST.

An optional tumor sample may be collected within 24 hours of the end of the infusion of NUC-1031 on C1D1. Specific instructions on the collection and shipment of tissue samples will be provided in the Tumor Tissue Laboratory Manual.

Correlation of response to NUC-1031 with genomic, transcriptomic and proteomic tissue biomarkers of tumor sensitivity and resistance will be assessed both in the freshly obtained tumor specimens and in archival samples obtained at screening. Markers of interest include cytidine deaminase (CDA), deoxycytidine kinase (dCK), human equilibrative nucleoside transporter 1 (hENT1), ribonucleotide reductase M1 (RRM1) and RRM2.

7.4 Labeling and Confidentiality of Biological Samples

All biological samples (including blood, urine and tumor) sent to analytical laboratories will be labeled with the study number, patient number and date/time taken. Samples labels must not contain any personally identifiable information.

7.5 Withdrawal of Consent for Biological Sample Collection or Retention

A patient may withdraw consent to provide samples or allow their samples to be used for research at any time without giving a reason. The Investigator must ensure that their wishes are recorded in the medical record and CRF. The CRO should be informed accordingly. The Investigator should discuss with patients the valuable use of samples that have already been provided and under circumstances where these samples have already been processed and anonymized, it would not be possible to destroy such samples.

8 INVESTIGATIONAL MEDICINAL PRODUCT

8.1 NUC-1031 Description

The drug product, NUC-1031 (for injection), is presented as a sterile solution in clear glass vials at a concentration of 250 mg/ml formulated in dimethylacetamide (DMA) and Normal Saline (0.9%) in the ratio of 80:20.

8.2 NUC-1031 Supplies and Study Drug Packaging

NUC-1031 will be supplied to the pharmacy of the investigative clinical site and will be supplied as a 7 ml fill volume in 10 ml clear glass vials. The vials are packaged in a labeled cardboard outer carton, each containing 6 vials.

A Diluent Solution is supplied as a 10 ml volume in clear glass 20 ml vials. The Diluent Solution is comprised of 20% DMA, 40% Kolliphor ELP and 40% Tween 80. The Diluent Solution vials are packaged in labeled cardboard outer carton, each containing 3 vials.

8.3 Handling and Storage

NUC-1031 and Diluent Solution must be stored in an appropriately secure Investigational Pharmacy at all times until dispensed for administration to patients on protocol. NUC-1031 must be stored between 2-8°C (36-46°F) in a temperature-monitored refrigerated unit. The Diluent Solution must be stored at room temperature (15-25°C/59-77°F). Only adequately trained pharmacy staff are permitted to handle NUC-1031 and the Diluent Solution. The study medication should not be removed from the pharmacy except for the purposes of dispensing to the patient for this protocol.

If NUC-1031 or the Diluent Solution contacts the skin or the mucous membranes, it should be washed immediately and thoroughly. For additional information on study drug handling including dispensing directions, please refer to the NUC-1031 Pharmacy Manual.

8.4 Preparation

As with other cytotoxic substances, applicable local procedures should be used in the preparation and administration of NUC-1031. Please refer to the administration guidance in the current version of the Pharmacy Manual and Administration Guidelines for further information on the preparation of NUC-1031.

8.5 Study Drug Dosage and Administration

NUC-1031 will be administered to each patient based on her body surface area (BSA) at baseline. If a patient's weight increases or decreases by $\geq 10\%$ during the course of the study, the dose of NUC-1031 should be recalculated. The Dubois & Dubois BSA calculation is the preferred method, however other standard calculations can also be used. Sites should document the method used in the eCRF.

Dubois & Dubois BSA calculation:

$$\text{BSA (m}^2\text{)} = 0.007184 \times \text{Height (cm)}^{0.725} \times \text{Weight (kg)}^{0.425}$$

Patients will receive IV NUC-1031 at an initial dose of 500 mg/m² or 750 mg/m² on Days 1, 8 and 15 of a 28-day schedule. Dose adjustments or dose delays are to be implemented within or between cycles based on drug related toxicities. The dose modification scheme to be employed is detailed in [Section 9](#) of this protocol.

The Diluent Solution (Kolliphor ELP; Tween 80; DMA) is provided for use by the hospital pharmacy to prepare NUC-1031 for administration by infusion in sterile saline for injection. The pharmacy will prepare the product for administration by mixing NUC-1031 and Diluent Solution and then further diluting the appropriate dose of this mixture in 0.9% sterile saline for injection. This preparation is then administered IV over 30 minutes. The administration time may be increased to 1 hour and then to 2 hours, if required. Please refer to the current Pharmacy Manual and Administration Guidelines for further information on NUC-1031 preparation and administration.

8.6 Drug Destruction

Used vials should be destroyed in accordance with local procedures and documented in the drug accountability and drug destruction log. A copy of the disposal certificates should be kept in the study file.

8.7 Study Drug Accountability

The FDA and other applicable regulatory authorities require accounting of all study drug received by each study center. Records of drug disposition required include the date received by the center, date administered, quantity administered, and the patient to whom study drug was administered. The Investigator is responsible for the accountability of all used and unused study drug containers and unused study drug. Each study center is to use a study drug

accountability log to document study drug disposition. All items on this form are to be completed in full.

The Investigator identification number and patient initials (as allowed by local regulations) and identification number are to be recorded on each study drug accountability log. Each time study personnel dispense study drug for a patient, he or she is to record the date dispensed, amount of study drug dispensed, Lot number, and the dispenser's initials. Study personnel are to monitor the inventory of clinical supplies and maintain a count of all used and unused study drug. The Sponsor's designated site monitor will review study drug accountability records and remaining drug supplies during routine monitoring visits.

8.8 Management of NUC-1031 Overdose

The dose of NUC-1031 intended for use on this protocol is 500 mg/m² or 750 mg/m². In the Phase I, FIH study, the highest dose studied was 1,000 mg/m². Should a substantial overdose occur, there is no known antidote. Any patient, who inadvertently receives a higher dose than intended should be monitored closely, managed with appropriate supportive care, including transfusion and hematopoietic growth factors as needed, until recovery. Such overdoses should be recorded as follows:

1. If an overdose occurs in the course of the study, site personnel must inform the Investigator and monitor immediately upon discovery of the event. An overdose will be recorded on the treatment CRF page and any associated AEs/SAEs will be recorded as the AE diagnosis/symptoms on the relevant AE/SAE page in the CRF. An overdose with no associated symptoms is only reported on the treatment CRF.
2. All overdoses should be tracked as a violation.

9 DOSE MODIFICATIONS

Adverse events may be managed by dose delays and/or dose reductions according to the clinical situation. Advice on how to modify dosing for hematological and non-hematological toxicities is given below.

Only one dose reduction is permitted within a cycle. This may be a temporary dose reduction, in which case the next cycle can revert to the starting dose of the previous cycle, or it may be a permanent dose reduction which would apply to all subsequent cycles. Over the whole dosing period, each patient may have a maximum of 2 permanent dose reductions, after which treatment will be discontinued. The lowest dose which may be administered is 275 mg/m².

Treatment between cycles can be delayed for up to 14 days in order for patients to meet the re-treatment criteria before starting their next cycle. Patients who do not meet these requirements after this additional time will not be allowed to receive further cycles of NUC-1031 and will be withdrawn from the study.

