9.1 Hematological Toxicity – Dose Adjustment

NUC-1031 administration should be given according to the absolute neutrophil count (ANC) and platelet count on the day of dosing. On Day 1 of each 28-day cycle, if the ANC is $\geq 1.5 \times 10^9/l$ and the platelet count is $\geq 75 \times 10^9/l$, then NUC-1031 should be given at full dose unless the patient has previously been permanently dose reduced.

On Day 1 of each 28-day cycle, if the ANC is $1.5-1.0 \times 10^9/l$ and the platelet count is $50-75 \times 10^9/l$ without evidence of bleeding, then NUC-1031 should be given at a reduced dose unless the patient has received 2 prior dose reductions.

Within a cycle, should patients experience neutropenia or thrombocytopenia, dosing on Day 8 and Day 15 should be adjusted per [Table 2](#).

Table 2 Dose adjustments within a cycle (Days 8 and 15) based on ANC and platelet counts

ANC		Platelets	Starting dose (750 mg/m ²)	Starting dose (500 mg/m ²)	Starting dose (375 mg/m ²)
$\geq 1.5 \times 10^9/l$	AND	$\geq 75 \times 10^9/l$	750 mg/m ²	500 mg/m ²	375 mg/m ²
1.5-1.0 $\times 10^9/l$ and afebrile	AND/OR	50-75 $\times 10^9/l$ without evidence of bleeding	500 mg/m ²	375 mg/m ²	275 mg/m ²
$<1.0 \times 10^9/l$, or $<1.5 \times 10^9/l$ with fever	AND/OR	$<50 \times 10^9/l$, or $<100 \times 10^9/l$ with active bleeding	Omit	Omit	Omit

Should both the Day 8 and Day 15 doses be omitted for hematologic toxicity within the same cycle, the dose for all subsequent cycles should be permanently reduced to the next dose level.

If a patient starts a treatment cycle at 500 mg/m² and requires further dose reduction on Day 8 or Day 15 of the following cycle due to hematologic toxicity, dose modification should follow the column second from the right of [Table 2](#).

If a patient has her dose permanently reduced to 375 mg/m², and hematologic toxicity persists on any day that a dose is scheduled, dose modification should follow the far right column of [Table 2](#).

For all other hematologic toxicity, dose adjustments should be performed according to [Table 3](#).

Table 3 Dose adjustments for hematological toxicities (excluding toxicities relating to ANC and platelet counts)

NCI CTCAE grade	Dose adjustment
Grade 1 toxicity	If the patient was receiving 750 mg/m ² then reduce to 500 mg/m ² . If the patient was receiving 500 mg/m ² then reduce to 375 mg/m ² . If the patient was receiving 375 mg/m ² then reduce to 275 mg/m ² .

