9.2 Non-Hematological Toxicity – Dose Adjustment

Dose adjustment should be performed according to [Table 4](#). If dose omission is required, treatment should be delayed until the toxicity has resolved to \leq Grade 1. If this occurs, subsequent doses should be permanently reduced, without re-escalation. For significant pulmonary complications (*e.g.* pneumonitis and acute respiratory distress syndrome), study treatment should be stopped.

Table 4 Dose adjustment for non-hematological toxicities

NCI CTCAE grade	Dose adjustment
Grade 0-2 toxicity or Grade 3 nausea/vomiting/ alopecia	100% dose (with escalation of anti-emetic prophylaxis for nausea and vomiting)
Grade 3/4 toxicity (except nausea/vomiting/alopecia)	Omit until resolution to \leq Grade 1 if the patient was receiving 750 mg/m ² then resume at the dose 500 mg/m ² . If the patient was receiving 500 mg/m ² then resume at the dose 375 mg/m ² . If the patient was receiving 375 mg/m ² then resume at the dose 275 mg/m ² .

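### For a 750 mg/m² starter already permanently reduced twice, Section 9 requires discontinuation while Sections 9.1 and 9.2 direct a further permanent step to 275 mg/m²

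*Protocol*

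**What the plan says.** Section 8.5 sets two initial doses: "Patients will receive IV NUC-1031 at an initial dose of 500" or 750 mg/m². One set of modification tables serves both.

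The opening of Section 9 gives three general rules:
- On the cap: "each patient may have a maximum of 2 permanent dose reductions, after which treatment will be discontinued".
- On the floor: "The lowest dose which may be administered is 275" mg/m², with no link to a starting dose.
- On within-cycle reductions: "This may be a temporary dose reduction, in which case the next cycle can revert to the starting dose of the previous cycle". Alternatively it may be permanent. The cap counts only permanent reductions.

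Section 9.1 (hematological toxicity) contains three relevant instructions:
- The Day 1 rule for intermediate counts says that NUC-1031 "should be given at a reduced dose unless the patient has received 2 prior dose reductions".
- If the Day 8 and Day 15 doses of one cycle are both omitted, "the dose for all subsequent cycles should be permanently reduced to the next dose level".
- A patient permanently at 375 mg/m² with persisting toxicity is sent, on every scheduled dosing day, to the last column of Table 2, which gives 275 mg/m² or omission.

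Section 9.2 (non-hematological toxicity) says that after an omission "subsequent doses should be permanently reduced, without re-escalation". The Grade 3/4 row of Table 4 includes the case "If the patient was receiving 375" mg/m², for which the resumed dose is 275 mg/m². Table 3 has a 375 to 275 mg/m² step as well, but does not say whether it is temporary or permanent.

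**The concern.** The cap is a rule for each patient over the whole dosing period. The step-down instructions are keyed to the dose the patient is on now, or to the starting dose of the cycle, and not to the dose she was randomized to. The two can therefore give opposite answers for the same patient: discontinue, or resume one level lower.

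The first matter at stake is safety. The choice between stopping and re-dosing a patient with repeated toxicity would depend on which passage a site consults. The second concerns the Part I comparison. The protocol bases dose selection on safety, dosing intensity, PK and clinical activity, and this ambiguity can arise only in the 750 mg/m² cohort. Differing site practice would alter exposure and discontinuations in one cohort and not the other.

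**Working it through.** No sample-size or error-rate figure is involved. The check is a count of steps against the stated cap, followed by a comparison of the instructions.

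**Inputs.** The dose ladder in Tables 2 to 4 is 750, 500, 375, 275 mg/m². Initial doses are 750 or 500 mg/m² (Section 8.5). The cap is 2 permanent reductions (Section 9).

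**Step count.** Number the levels 750 = 0, 500 = 1, 375 = 2, 275 = 3. Permanent steps needed to reach 275 mg/m² = 3 − position of the initial dose, moving one level at a time.

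- Start 750: 3 − 0 = 3 steps (750→500, 500→375, 375→275). The dose after two steps is 375 mg/m². Since 3 > 2, the last step exceeds the cap.
- Start 500: 3 − 1 = 2 steps (500→375, 375→275). The dose after two steps is 275 mg/m². Since 2 = 2, the last step is within the cap.

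**Instructions for a 750 mg/m² starter who is at 375 mg/m² after two permanent reductions.**

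| Provision | What it directs | Permanent? | Limit for this patient? |
|---|---|---|---|
| Section 9, cap | Discontinuation; no third permanent reduction | n/a | Yes |
| Section 9.2 with Table 4 | Omit, then resume at 275 mg/m² | Yes, expressly | None stated |
| Section 9.1, Day 8 and Day 15 both omitted | Next level down (275 mg/m²) for all later cycles | Yes, expressly | None stated |
| Section 9.1, permanently at 375 mg/m², with Table 2 | 275 mg/m² or omit, on any scheduled dosing day | May be temporary | None stated |
| Section 9.1, Day 1 rule | No reduced dose after 2 prior reductions | Not stated | Yes |
| Table 3 | 275 mg/m² | Not stated | None stated |

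**Reading the rows together.**

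1. Row 1 conflicts directly with rows 2 and 3. Both of those order a permanent step, and for this patient it is her third. Whether the cap means stopping once the second reduction has been used, or stopping when a third is needed, a third permanent reduction is barred.
2. Rows 4 and 5 conflict with each other on Day 1. With counts in the intermediate range, the Day 1 rule withholds a reduced dose from a patient with two prior reductions, while the instruction for patients permanently at 375 mg/m² covers every dosing day and leads to 275 mg/m². The title of Table 2 limits it to Days 8 and 15, which adds to the uncertainty.
3. Rows 4 and 6 do not by themselves contradict the cap, because the reduction may be temporary (Table 2) or is unspecified (Table 3).

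**The case against.** The strongest reply is that the cap opens Section 9, applies to each patient, and governs everything after it. On that view the tables are ladders used inside the cap. One set serves both initial doses, so a 375 to 275 mg/m² row has to appear for 500 mg/m² starters and need not repeat a patient-level limit. The Day 1 rule shows how the limit and a reduction instruction are meant to be combined.

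Much of this stands. The row is not an error in itself, and a careful site could count reductions and stop at the cap. But the reading is not secure. Only the Day 1 rule repeats a limit, and it omits the word permanent. The two instructions that order a permanent reduction carry no limit, and a site could reasonably infer that none applies there. The list of reasons for ending treatment in Section 6.1 does not include reaching two permanent reductions. For a significant drug-related event that recurs despite dose reduction in two consecutive cycles, it even allows treatment to continue by agreement.

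A reader might also infer more than the documents support:
- *That every 375 to 275 mg/m² step is a forbidden third reduction for 750 mg/m² starters.* It is not. Such a patient may be permanently at 500 and only temporarily at 375 mg/m², with one permanent reduction counted.
- *That up to 20 Part I patients, or all 44 evaluable patients if 750 mg/m² is selected, are affected.* Those figures cover everyone on that dose. The conflict needs two permanent reductions and then a further toxicity. Section 9 allows one reduction per cycle, so a third falls no earlier than the third cycle. In the Phase I study the median was 3 cycles across doses (Section 1.4.2), and Section 3.2 reports that patients at 750 mg/m² and below largely kept their treatment intensity.
- *That the response-rate endpoint is compromised.* Nothing in the protocol shows an effect on confirmed ORR.

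**Conclusion.** The point holds in a narrow form. For a 750 mg/m² starter with two permanent reductions, the Section 9 cap conflicts with Section 9.2 and Table 4, and with the Section 9.1 rule for omission of both the Day 8 and Day 15 doses. Within Section 9.1, the Day 1 limit also conflicts with the instruction for patients permanently at 375 mg/m². The size is one step: three permanent reductions to reach 275 mg/m² against a stated maximum of two. For 500 mg/m² starters there is no excess.

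This assumes permanent reductions taken one level at a time, as the tables prescribe. The number of patients who would meet the conflict cannot be estimated from the protocol and may be small. An influence on Part I dose selection is possible but not demonstrated. The wording should still be corrected, because the conflict decides whether an individual patient is re-dosed or stopped and the correction is cheap.

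**What to change.** Reconcile the opening of Section 9, Sections 9.1 and 9.2, and Tables 2 to 4 so that, for each starting dose, the number of permanent reductions allowed, the lowest level and the point of discontinuation are the same wherever they appear. State how the cap applies to the Section 9.2 reduction and to the rule for omission of both Day 8 and Day 15. State also whether the Table 3 reductions and the Day 1 limit refer to permanent reductions, and whether the last column of Table 2 applies on Day 1. Which rule is adopted is a clinical decision for the sponsor, and none is proposed here.

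The cost is wording in a protocol amendment and notice to sites. No change to sample size, endpoints or analyses is needed.

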- 17.** For women of child-bearing potential, serum pregnancy testing must be performed within 72 hours prior to C1D1 and at End of Treatment visit. In addition, urine pregnancy tests will be performed pre-dose on Day 1 of each cycle. If any urine test result is positive, patient dosing will be postponed until the result is confirmed by a serum pregnancy test. Patients with a positive serum test will be discontinued from the study.
- 18.** Includes insertion of central venous access device, if not already present (if NUC-1031 is centrally administered).
- 19.** Optional fresh biopsy tissue sample collection within 24 hours post administration of C1D1 dose for patients who consent.
- 20.** Includes treatment discontinuation due to disease progression or early treatment discontinuation for other reasons (*e.g.* withdrawal of consent). Progressive disease should be confirmed prior to stopping treatment. Visit to occur within 30 (± 7) days of the last dose of NUC-1031.
- 21.** Patients withdrawing from the study with no radiological evidence of disease progression will receive scans every 8 weeks (± 7 days) from C1D1 until disease progression, initiation of a new treatment or death in order to determine duration of overall response and PFS.
- 22.** Adverse events should be captured from the time of consent up to 30 days after the last dose of NUC-1031. SAEs deemed definitely, probably or possibly related to NUC-1031 but outside of this window (>30 days from last dose of NUC-1031) should also be captured in the eCRF.
- 23.** Patients with evidence of disease progression as defined by RECIST criteria will receive a phone call at regular intervals (every 12 weeks ± 7 days) until death, loss to follow-up, or study discontinuation in order to determine duration of Overall Survival.

ABBREVIATIONS

°C	Degrees Centigrade
AE	Adverse event
ALT	Alanine aminotransferase
ANC	Absolute neutrophil count
AST	Aspartate aminotransferase
AUC	Area under the curve
AUC _{0-t}	Area under the plasma concentration-time curve from time zero to the last measurable concentration
BICR	Blinded Independent Central Reviewer
BRCA 1/2	Breast cancer (gene) 1/2
BUN	Blood urea nitrogen
CA125	Cancer Antigen 125
CDA	Cytidine deaminase
CL	Apparent clearance
C _{max}	Maximum plasma concentration; peak plasma concentration
CNS	Central Nervous System
CR	Complete Response
CRF	Case report form
CRO	Clinical Research Organization
CSR	Clinical study report
CT	Computed tomography

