6 PATIENT WITHDRAWAL

6.1 End of Treatment

Treatment with NUC-1031 is to be continued until one of the following occurs:

- Progressive Disease (PD) as defined by RECIST criteria. Patients should not discontinue NUC-1031 because of raised CA125 or other clinical signs of PD until PD has been confirmed by RECIST.
- Unmanageable toxicity defined as an AE that is considered by the Investigator to warrant permanent discontinuation of NUC-1031 including the following:
 - AE resulting in a dosing delay of more than 14 days in starting the next cycle, unless the patient is receiving clinical benefit.
 - Clinically significant drug-related AE that recurs despite dose reduction in two consecutive cycles. Patients may continue to receive treatment if the Principal Investigator and Medical Monitor agree that the patient is receiving a clinical benefit and the toxicity is manageable, reversible or transient.
- Lack of further clinical benefit or unfavorable risk/benefit profile as judged by the Investigator.
- Inter-current illness that prevents further administration of NUC-1031.
- Patient withdraws consent from further treatment or for further data collection.
 - If the patient withdraws consent for further treatment, follow-up visits should continue.
 - If the patient withdraws consent for further treatment and data collection, then no additional study visits or data collection should occur.
- Patient requires use of a prohibited concomitant medication or therapy.
- Pregnancy.
- Changes in the patient's condition, which in the opinion of the Investigator, make the patient unsuitable for further treatment with NUC-1031.
- Patient non-compliance.
- Lost to follow-up.
- Patient withdrawal of consent.
- Sponsor request.

All study procedures outlined for the End of Treatment visit are to be completed within 30 days (± 7 days) of the last dose of study drug. The primary reason for study drug discontinuation is to be recorded in the CRF.

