6.2 Follow-Up After Treatment Discontinuation

Patients who have documented disease progression defined by RECIST criteria while receiving study medication will discontinue treatment but will enter the follow up period. Patients should not discontinue NUC-1031 because of raised CA125 or other clinical signs of PD until PD has been confirmed by RECIST.

Patients who stop treatment with no evidence of disease progression will enter the follow-up period and should attend clinic every 8 weeks (± 7 days) from C1D1 for follow-up scans and assessments. This should continue until disease progression, initiation of a new treatment or death.

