6.3 Consent Withdrawal

Patients will be informed that they have the right to withdraw from the study at any time for any reason, without prejudice to their medical care.

Consent withdrawal means that a patient has expressed a wish to withdraw from the study altogether. Under these circumstances, the site personnel should document all relevant discussions in the patient notes and mark all future CRF pages as not applicable. Under these conditions, Investigators are still responsible to follow up any SAEs until resolution.

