12.9 Pregnancy

Patients who become pregnant should be withdrawn from study treatment immediately. Pregnancies (in a patient or partner) occurring during the study require expedited reporting. A Pregnancy Notification Report should be completed and submitted to Chiltern PV within the same timelines and using the same contact details as an SAE. All reported pregnancies should be followed up and the outcome reported using the Pregnancy Follow-up Report. If the outcome of the pregnancy meets any of the criteria for seriousness, it must also be reported as an SAE.

Examples of pregnancy outcomes that are SAEs include reports of:

- Congenital anomalies or developmental delay, in the fetus or the child.

- Fetal death and spontaneous abortion.
- Suspected adverse reactions in the neonate that are classified as serious.

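### Section 9 withdraws patients from the study after a failed 14-day delay, while Sections 3.4, 5.5.8, 6.2 and 11.1 keep patients who stop drug without progression on 8-weekly scans

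*Protocol*

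**What the plan says.** **Section 9 (Dose Modifications).** A new cycle may be delayed by up to 14 days. Patients who still do not meet the re-treatment requirements "will not be allowed to receive further cycles of NUC-1031 and will be withdrawn from the study". The sentence imposes two consequences: no more drug, and departure from the study.

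**Section 6.1 (End of Treatment).** Among the reasons to end treatment is "AE resulting in a dosing delay of more than 14 days in starting the next cycle, unless the patient is receiving clinical benefit". This concerns treatment only, and it carries an exception that Section 9 lacks.

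**Section 6.2 (Follow-Up After Treatment Discontinuation).** "Patients who stop treatment with no evidence of disease progression will enter the follow-up period and should attend clinic every 8 weeks". Sections 3.4, 5.5.8 and 11.1 say the same in substance: a patient who stops drug without progression continues to be scanned every 8 weeks, counted from Cycle 1 Day 1.

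**Summary Schedule of Events, note 21.** Patients who withdraw from the study without radiological progression still receive 8-weekly scans. Here, withdrawal from the study does not end assessment.

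**Pregnancy.** Note 17 of the schedule says "Patients with a positive serum test will be discontinued from the study", while Section 12.9 says "Patients who become pregnant should be withdrawn from study treatment immediately".

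**The concern.** Stopping the drug and leaving the study are different events, and the protocol does not keep them apart. For a patient whose toxicity has not resolved after 14 days, Section 9 read alone tells the site that she has left the study. Section 6.2 tells the same site to keep scanning her.

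Two things are at stake if a site follows Section 9.

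- **Confirmed response.** Section 11.1 requires a repeat image at least 4 weeks after a response is first documented, and the primary endpoint counts only confirmed responses. In Appendix 2, Table 2, a PR followed by a non-evaluable time point is scored as SD or NE, not PR.
- **Time-to-event endpoints.** Under Section 13.5.4, PFS is censored at the last progression-free observation, and time to progression and duration of response at the last tumor assessment. Scans that end because of a toxicity stop would make that censoring related to toxicity and possibly to prognosis.

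**Working it through.** **1. The passages side by side, for one patient who misses re-treatment criteria after 14 days and has not progressed.**

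| Place | Drug | Scans |
|---|---|---|
| Section 9 | stops | withdrawn from the study; scans not mentioned |
| Section 6.1 | ends, unless there is clinical benefit | not stated for this trigger |
| Sections 3.4, 5.5.8, 6.2, 11.1 | stopped | every 8 weeks from Cycle 1 Day 1 |
| Note 21 | not addressed | every 8 weeks, even when withdrawing from the study |

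Section 9 agrees with the others on scans only if withdrawal from the study is read in the sense of note 21. Section 6.3 uses leaving the study in the opposite sense: there, data collection ends. A site has no definition to choose by.

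**2. Can the conflict fall between a response and its confirmation?** Take two 28-day cycles given on time.

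- First scan and due date of cycle 3: 2 × 28 = 56 days, week 8. Suppose a PR is seen.
- End of the permitted delay: 8 + 2 = week 10.
- Earliest confirming image: 8 + 4 = week 12.
- Next scheduled scan: 8 + 8 = week 16.

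The Section 9 decision at week 10 comes before either confirming image. The case is an ordinary one on the protocol's own calendar.

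**3. What lost confirmations would do to the primary rule.** Section 13.1 has 44 patients, success at 4 or more confirmed responses, and a stated probability above 80% at a true ORR of 15%. The exact binomial gives P(X ≥ 4) = 0.913 for X ~ Bin(44, 0.15), consistent with that statement. (The companion statement, below 7% at a true rate of 5%, is not reproduced: 4 or more gives 0.177 and 5 or more gives 0.067. That is a separate matter and the present point does not rest on it.)

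Let q be the share of true responders who lose confirmation but stay in the denominator. The confirmed rate is then 0.15 × (1 − q). **The documents give no value for q, so the values below are assumptions.**

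| q (assumed) | Confirmed rate | P(X ≥ 4) |
|---|---|---|
| 0 | 0.150 | 0.913 |
| 5% | 0.1425 | 0.890 |
| 10% | 0.135 | 0.862 |
| 20% | 0.120 | 0.790 |

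The expected number of responders at 15% is 44 × 0.15 = 6.6, so q = 5% means about 0.3 of a patient and q = 20% about 1.3. In a single trial the effect is simple: 4 responses with one left unconfirmed become 3, and the rule is missed.

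**The case against.** The strongest reply is that the protocol's intention is clear. Four sections require continued scanning, and note 21 applies that requirement to patients described in nearly the same words as Section 9. Section 6 is itself titled Patient Withdrawal and opens with End of Treatment, which suggests that withdrawal is often shorthand for stopping drug. A careful site would keep scanning. This stands, and it limits the point to a risk from wording. It does not remove the contradiction, because Section 9 names leaving the study as a consequence in addition to stopping drug.

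A reader might infer more than the documents support:

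- **That every such patient loses all later scans.** Note 21 and Sections 3.4, 5.5.8, 6.2 and 11.1 say otherwise.
- **That the loss is greater at 750 mg/m² and distorts dose selection.** Section 3.2 puts the more substantial delays at 825 mg/m² and above and says that patients at 750 mg/m² and below largely kept their intensity. Sections 13.3 and 13.5.7 also allow responses that are unconfirmed for lack of follow-up to count in dose selection.
- **That Section 6.3 contradicts Section 6.1.** Section 6.1 says "If the patient withdraws consent for further treatment, follow-up visits should continue", and Section 6.3 says "Consent withdrawal means that a patient has expressed a wish to withdraw from the study altogether". By its own definition, Section 6.3 does not reach a patient who declines drug but accepts follow-up, and it concerns consent, not toxicity.
- **That Section 9 is what ends survival follow-up.** Calls run "until death, loss to follow-up, or study discontinuation in order to determine duration of Overall Survival", but Section 5.5.8 and note 23 assign them only to patients with RECIST progression. Survival follow-up of patients who stop drug without progression is weakly specified whatever Section 9 says.
- **That a number of affected patients can be given.** No rate of such stops is stated.

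One further limit applies. Appendix 2 classifies best response up to the end of treatment, so the standing of a confirming scan taken after the drug has stopped is not fully clear, although Section 11.1 does require response assessment to continue.

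**Conclusion.** Section 9 is wrong as written, because it cannot be reconciled with Sections 3.4, 5.5.8, 6.2 and 11.1 on what follows a treatment stop. The consequence is possible but not certain: a site applying Section 9 literally could miss a confirming scan and could introduce toxicity-related censoring into PFS, time to progression and duration of response. The size cannot be stated from the documents, and neither can the direction of any bias in the time-to-event estimates. The fall from 0.913 to between 0.890 and 0.790 rests on an assumed 5% to 20% of responders losing confirmation, independently and with all 44 patients kept in the denominator. It shows sensitivity and is not a forecast. The correction is worth making because it protects the primary endpoint at almost no cost.

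**What to change.** 1. **Section 9.** Replace the wording on withdrawal from the study by a statement that a patient whose treatment ends under this rule discontinues study treatment and enters follow-up as described in Section 6.2.
2. **Summary Schedule of Events, note 21.** Refer to patients stopping treatment instead of patients withdrawing from the study.
3. **Reconcile, for the sponsor to decide.** Note 17 and Section 12.9 differ on whether pregnancy ends study participation or only treatment. Sections 9 and 6.1 differ on the clinical-benefit exception after a delay of more than 14 days. This review takes no view on which clinical rule applies.

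The first two items are changes of wording in two places. They do not alter when drug is stopped and add no visits, since the scans are already required of patients who stop treatment without progression. The third needs a sponsor decision and the matching text edits.
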